### 9b. Exclusion criteria

Exclusions from **ALL** Procedures:

- Populations
  - Inability to give informed consent (a diminished understanding or comprehension);
  - Inability to travel to Outpatient Facility;
  - Pregnant women;
  - Prisoners; and
  - Children, under the age of 16 years old
- Active Smoker - Active smoking prevalence has been estimated at:
  - Nationally: 17.8 %
  - Texas: 15.9 %
  - Dallas County: 15.3 %
  - Denton County: 10.1 %
  - Collin County: 9.7 %
- Currently diagnosed with cancer or have had cancer within the past 5 years.
  - Current cancer prevalence is estimated by the National Cancer Institute at 3.7% for males in Texas and 3.9% for females in Texas. National cancer cases were estimated in 2010 to be 13,772,000 nationally for a prevalence rate of 4.5% of the estimated national population of 309,300,000.
- Identification of new nodules/masses per chest x-ray/CT scan report that have not been noted as stable.
  - Documentation of stability must be received for confirmation prior to treatment.
- Active Infection (pulmonary or other);
- Active Tuberculosis
- A History of Recent Hospitalization (requiring mechanical ventilation in a period of one month before treatment);
- End Stage Kidney Failure;
- Acute Heart Failure; and/or
- Other Condition(s) the Provider or Principal Investigator feels would interfere with treatment protocols.

Rev\_2/5/16 Page 4 of 10

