### 13. RISK AND BENEFIT ANALYSIS

All measures are taken to minimize or mitigate risks to the patient. The following lists the potential risks as indicated on the patient informed consent:

- **Adverse reaction to stem cells** - There is a possibility of an adverse reaction to the application of stem cells. This risk is minimized by using autologous (your own) unaltered stem cells.
- **Anemia** - There have been reports of anemia with harvesting of stem cells from the circulation. This risk is low. To minimize this risk we request blood work (CBC).
- **Embolus development** - An embolus is a clot that may be from blood or cells such as fat or bone marrow. There is a chance that an embolus or emboli (plural) may develop with stem cell procedures. This risk is low and is minimized due to our stem cells processing protocols.
- **Failure of the procedure** - There is a chance that undergoing stem cell application will not alleviate symptoms, resolve inflammation, or assist in regenerating tissue.
- **Fever** - Fever associated with stem cell harvesting usually responds to acetaminophen. If fevers persist, a work-up for infection must be completed.
- **Infection** - Infection may occur at the donor site where the bone marrow or fat was harvested or at the IV site and recipient site of application. To minimize risk infection prevention protocols are maintained and followed during the treatment process and patient education is provided on post treatment cleaning and wound care.
- **Pain** - Any procedure can result in pain. To minimize this risk we ask that our patients communicate any discomfort so that we can reduce or mitigate.
- **Numbness/tingling** – Although a low risk, this has been reported with leukapheresis (the process of separating stem cells from peripheral blood in the vein). Laboratory analysis may be required along with calcium infusion.
- **Respiratory difficulties** - Breathing difficulties (which are usually temporary) or post-operative pneumonia, may occur as a result of any procedure or surgery. Pulmonary embolus, a blood clot causing blockage of an artery in the lungs may occur as a result of any procedure or surgery. Pulmonary embolus may be fatal.
- **Stroke** - Though a low risk and unlikely, there is a possibility that a stroke will occur during the procedure or in the recovery period.

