**2. RULE-OUTS FOR *VENOUS* PROCEDURE**

- a) ACTIVE TUBERCULOSIS;
- b) HISTORY OF CANCER (WITHIN THE PAST 5 YEARS);
  - i. ON A CASE-BY-CASE BASIS, PROVIDER MAY APPROVE PROCEDURE(S) FOR NON-AGGRESSIVE/NON-ACTIVE CASE(S).
- c) IDENTIFICATION OF NEW NODULES/MASSES PER CHEST X-RAY/CT SCAN REPORT THAT HAVE NOT BEEN NOTED AS STABLE.
  - i. DOCUMENTATION OF STABILITY MUST BE RECEIVED FOR CONFIRMATION PRIOR TO TREATMENT.
- d) ACTIVE INFECTION (PULMONARY OR OTHER);
- e) A HISTORY OF RECENT HOSPITALIZATION (REQUIRING MECHANICAL VENTILATION IN A PERIOD OF ONE MONTH BEFORE TREATMENT);
- f) END STAGE KIDNEY FAILURE;
- g) ACUTE HEART FAILURE; AND/OR
- h) OTHER CONDITION(S) THE PROVIDER OR PRINCIPAL INVESTIGATOR FEELS WOULD INTERFERE WITH TREATMENT PROTOCOLS.

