
10.
	
Clinic Staff conducts introductions, reviews process, and checks for Patient readiness.
 
 
• Has Clinic Staff introduced themselves? 
 
✓ Name and Roles
 
 
 
• Has Clinic Staff reviewed the procedure process for the day? 
 
✓ Go over what the Patient can expect during the days procedure
 
 
 
• Has Clinic Staff ensured Patient readiness? 
 
✓ Answer any questions the Patient may have; and
 
✓ Check to see if Patient needs to use the restroom prior to procedure.
 
 
 
 
➤ If NO > Step must be completed prior to proceeding.
 
➤ If YES > Proceed to Step 11 of this SOP

11.
	
Clinic Staff obtains vitals.
 
 
• Has Clinic Staff obtained the following vitals? 
 
✓ Blood Pressure;
 
✓ Pulse;
 
✓ Heart Rate;
 
✓ Respiratory Levels;
 
✓ SaO Levels;
 
✓ EKG (If required, per Practitioner's judgement); and
 
✓ PFT (May be obtained within the 3 days of scheduled treatment)
 
 
 
 
➤ If NO > Obtaining Patient vitals is required prior to proceeding.
 
➤ If YES > Proceed to Step 12 of this SOP

12.
	
Clinic Staff completed the subjective/chief complaint.
 
 
• Has Clinic Staff completed the Subjective/Chief Complaint? 
 
✓ Patient Complaint/Primary Reason for Visit (i.e.: Patient here for shortness of breath, second day of procedure, COPD Treatment, etc.)
 
 
 
 
➤ If NO > Step must be completed prior to proceeding.
 
➤ If YES > Proceed to Step 13 of this SOP

10Mar2016 - version 2.0

LI-001

13.
	
Is today the first treatment day for the Patient?
 
➤ If NO > Proceed to Step 16 of this SOP
 
➤ If YES > Proceed to Step 14 of this SOP

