8.	
Has Clinic Staff conducted introductions, review process, and checks for readiness?
 
 
• Clinic Staff introduces themselves; 
 
✓ Name and Roles
 
 
 
• Reviews the procedure process for the day; and 
 
✓ Go over what the Patient can expect during the days procedure
 
 
 
• Ensure Patient readiness 
 
✓ Answer any questions the Patient may have; and
 
✓ Check to see if Patient needs to use the restroom prior to procedure.
 
 
 
 
➤ If NO > Preparation is required prior to proceeding.
 
➤ If YES > Proceed to Step 9 of this SOP

9.	
Clinic Staff obtains vitals.
 
 
• Has the Clinic Staff obtained Patient Vitals? 
 
✓ Blood Pressure;
 
✓ Pulse;
 
✓ Heart Rate;
 
✓ Respiratory Levels;
 
✓ SaO Levels;
 
✓ EKG (Required to be obtained prior to Bone Marrow Procedure); and
 
✓ PFT (May be obtained within the 3 days of scheduled treatment)
 
 
 
 
➤ If NO > Obtaining Patient vitals is required prior to proceeding.
 
➤ If YES > Proceed to Step 10 of this SOP

10.	
Clinic Staff completed the subjective/chief complaint.
 
 
• Has Clinic Staff completed the Subjective/Chief Complaint? 
 
✓ Patient Complaint/Primary Reason for Visit (i.e.: Patient here for shortness of breath, second day of procedure, COPD Treatment, etc.)
 
 
 
 
➤ If NO > Step must be completed prior to proceeding.
 
➤ If YES > Proceed to Step 11 of this SOP

11.	
Is today the first treatment day for the Patient?
 
➤ If NO > Proceed to Step 13 of this SOP
 
➤ If YES > Proceed to Step 12 of this SOP

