6.	
Clinic Staff must properly prepare mayo stand under a clean technique for Patient procedure.
 
 
• Has the Clinic Staff prepared the mayo stand by covering with underpad and ensuring all the following is made available? 
 
✓ 30ml Syringe with ACD-A
 
✓ 20g or 22g IV Catheter
 
✓ Alcohol Prep Pad(s)
 
✓ 2x2 Gauze
 
✓ IV Starter Kit
 
 
 
• Has the Clinic Staff hung the IV bag in the exam room on the IV pole? 
 
✓ Previously spiked 100ml Normal Saline (NS) IV Bag
 
 
 
 
 If NO > Preparation is required prior to proceeding.
 
 If YES > Proceed to Step 7 of this SOP

7.	
Clinic Staff obtains vitals.
 
 
• Vitals: 
 
✓ Blood Pressure;
 
✓ Pulse;
 
✓ Heart Rate;
 
✓ Respiratory Levels;
 
✓ SaO Levels;
 
✓ EKG (If required, per Practitioner's judgement); and
 
✓ PFT (May be obtained within the 3 days of scheduled treatment)
 
 
 
 
➤ If NO > Obtaining Patient vitals is required prior to proceeding.
 
➤ If YES > Proceed to Step 8 of this SOP

8.	
Clinician draws blood and affixes IV line to catheter.
 
 
• IV site is prepped and disinfected;
 
• Affix tourniquet to upper arm;
 
• Insert IV catheter into desired site;
 
• Remove needle from catheter;
 
• Affix Harvest PRP kit 30ml syringe to catheter and draw approximately 30ml of blood;
 
• Remove syringe and affix IV drip line to catheter;
 
• Check the patency and flow to make sure it is correct;
 
• Once correct, close off IV drip line until reinfusion; and
 
• Dispose of supplies in designated biohazard/sharps containers.
 
 
➤ If NO > Step must be completed prior to proceeding.
 
➤ If YES > Proceed to Step 9 of this SOP

10Mar2016 - version 2.0

LI-001

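### No vitals checklist requires a temperature, so fever is not systematically measured, although active infection is an exclusion and fever a named risk

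*Combined protocol and SAP*

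**What the plan says.** Four checklists govern vital signs. Venous SOP Step 11 asks "Has Clinic Staff obtained the following vitals". Bone Marrow SOP Step 9 and Discharge SOP Step 15 (bone marrow branch) ask "Has the Clinic Staff obtained Patient Vitals". Discharge SOP Step 7 (venous branch) is headed "Clinic Staff obtains vitals". Each then itemizes what to take. Each is also a gate: where the answer is no, "Obtaining Patient vitals is required prior to proceeding".

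Active infection is an exclusion for all procedures in protocol Section 9b ("Active Infection (pulmonary or other"). Policy CL-005 repeats it among the rule-outs for both the venous and the bone marrow procedure.

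Section 13 lists fever and infection as risks. On fever it says "Fever associated with stem cell harvesting usually responds to acetaminophen" and then requires an infection work-up if fever persists.

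Safety is the first research question (Section 4). The secondary hypothesis in Section 5b is that no adverse events will be reported. Section 6 says that safety data will be tracked and reported separately as a descriptive, quantitative analysis. Section 12b, on statistical methods, covers FEV1 and quality of life and gives no method for adverse events.

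**The concern.** Fever is an event that the plan itself predicts, and it is established by one simple reading. The lists that decide whether a patient may proceed do not ask for that reading. Staff can answer yes, complete the step and move on to infusion without it.

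Three things are at stake.

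- **Counting.** Fever that is not routinely measured is recorded only when a patient mentions it or a practitioner happens to take a temperature. The safety hypothesis is the absence of reported events, so incomplete ascertainment leans toward that hypothesis.
- **Attribution.** Without a required value before infusion, a fever found later cannot reliably be classed as new or already present.
- **Eligibility on the day.** The infection exclusion has no objective same-day measurement behind it. It depends on an exam whose content is not set out.

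**Working it through.** No arithmetic applies and the plan gives no figure to reproduce. The check sets the four lists side by side and then looks for any other same-day step that would capture fever or infection.

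**The vitals lists**

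| Checklist | Position | Both pulse and heart rate | EKG | Temperature |
|---|---|---|---|---|
| Venous SOP, Step 11 | Before infusion (Step 20) | Yes | If the practitioner asks | No |
| Bone Marrow SOP, Step 9 | Before aspiration (Step 29) and infusion (Step 39) | Yes | Always ("EKG (Required to be obtained prior to Bone Marrow Procedure); and") | No |
| Discharge SOP, Step 7 (venous) | Before that day's infusion (Step 11) | Yes | If the practitioner asks | No |
| Discharge SOP, Step 15 (bone marrow) | Visit after marrow treatment | Yes | If the practitioner asks | No |

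Temperature is in 0 of 4 lists and appears nowhere else in the text supplied. The bone marrow list was adapted to its procedure, since its EKG is mandatory, but a temperature was not added there either.

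**Other steps that could detect infection or fever**

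- *Laboratory and imaging review* (Step 2 of the Venous and Bone Marrow SOPs): a blood count with differential and chest imaging. The preferred window is 6 months for venous and 3 months for bone marrow, so this is not a same-day check.
- *Review of systems* (Venous Step 14, Bone Marrow Step 12): first treatment day only, and it is history rather than measurement.
- *Practitioner exam* (Venous Step 18, Bone Marrow Step 15): before infusion, with a written note. In the venous SOP both the first-day and later-day paths lead to Step 18. The content of the exam is not specified, and no temperature is required.
- *Physical assessment* (protocol Section 11): required before marrow aspiration and before venous administration. Its content is also unspecified.
- *Incision check* (Discharge Step 16): staff look for infection at the wound and call the practitioner to examine it. This covers the bone marrow branch only, and the vitals in the step before it omit temperature.

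**The venous discharge branch**

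The sequence is vitals (Step 7), blood draw (Step 8), processing (Step 9), extraction (Step 10) and infusion (Step 11). Step 9 tells the practitioner that the patient can be seen, and Step 14 asks whether the practitioner was available for education and questions. No exam step is listed. Section 11 requires a physical assessment before venous administration, so the SOP and the protocol do not match here.

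**After the clinic days**

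The first scheduled contact is at 2 weeks, with later contacts at 3 and 6 months. Section 11 makes the calls voluntary, and CL-005 part H allows two attempts for each. The clinic days are therefore the main scheduled opportunity for an objective reading.

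**The case against.** The strongest reply is that a list without temperature does not contradict an infection exclusion supported by an exam. The documents provide several exams, adverse events go to the Principal Investigator by whatever route they surface, and nothing forbids a practitioner from taking a temperature. Two of the lists ask generally about patient vitals before itemizing them. The EMR steps in the Venous and Bone Marrow SOPs also refer to checklists and flowsheets that are not in the text supplied. All of this stands, and it limits the point to what is required and recorded.

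Several stronger readings are tempting, and the documents do not support them.

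- A reader might infer that neither infection nor fever can be checked on any treatment or discharge day. That is not so: Section 11, Venous Step 18, Bone Marrow Step 15 and Discharge Step 16 all provide for assessment or examination.
- A reader might infer that fever reaches the safety data only through patient report. A practitioner may also find it.
- A reader might infer that venous patients go unexamined on discharge day. The SOP branch lists no exam step, but the Section 11 requirement still applies.
- A reader might multiply the 200 anticipated patients by two clinic days. No passage sets a minimum number of days for every patient, and the product would count readings, not missed fevers or infections.
- A reader might treat pulse and heart rate as duplicates and drop one to make room. No passage says that they are interchangeable.

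It is also fair to say that these checks come before infusion or at the next visit. A temperature taken there cannot detect a fever that begins at home.

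**Conclusion.** The point holds in a limited form. None of the four vitals checklists requires temperature, although active infection is an exclusion and fever is a named risk with a work-up attached. Fever is therefore not systematically measured or recorded before infusion or at the next clinic day, and same-day infection screening rests on an exam of unspecified content. The venous discharge branch also needs reconciling with Section 11.

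The extent in the documents is 4 of 4 lists. The effect on the safety results has a direction, toward fewer recorded events, but no size: the documents give neither a fever rate nor the share of fevers that an exam or a patient's report would find.

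Two assumptions matter. The first is that staff work to the lists as written; if temperatures are taken anyway or sit on a flowsheet not supplied, the gap is in the written plan more than in practice. The second is that the four lists are all that apply; Section 11 also names an adipose SOP, which is not in the text supplied and could not be examined.

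This is a cheap correction to safety ascertainment that should be made. It does not invalidate the study.

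**What to change.** 1. Add a temperature entry to Venous Step 11, Bone Marrow Step 9 and Discharge Steps 7 and 15, and keep every existing item.
2. Capture it with the vitals that staff already enter in the EMR (Venous Step 25, Bone Marrow Step 43, Discharge Step 20). No new recording process is needed.
3. State in Section 12b that the descriptive safety analysis will report fever, with the number of patients who had a temperature recorded at each check and the pre-infusion value beside any later one. Also state that these readings do not cover the period after discharge, for which the follow-up contacts remain the source.
4. Reconcile the vitals lists with the infection exclusion and the fever risk, and reconcile the venous discharge branch with the physical assessment required by Section 11.

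Any temperature limit, and any action that follows from it, is for the clinic to set; none is proposed here. The cost is four checklist lines across three SOPs, a short addition to Section 12b, and seconds per visit.

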## 1. INTRODUCTION

The purpose of the Lung Institute is to collect and process a patient's own stem cells and platelet rich plasma (PRP) and deliver them back to the patient same-day through an intravenous catheter and sometimes by nebulizer. Lung Institute's treatment is limited to self-funded patients with chronic lung diseases – chronic obstructive pulmonary disease (COPD) and interstitial lung disease (ILD). The patient's stem cells and platelet rich plasma are collected through venous, adipose or bone marrow harvesting techniques. After the stem cells and platelet rich plasma have been isolated they are administered back to the patient. An inhaled antioxidant, glutathione, is administered during treatment to help mobilize lung secretions.

Researchers have demonstrated that using autologous stem cells (those derived from the patient) with minimal manipulation is safe and effective to promote the healing of lung tissue affected by COPD and ILD. The administration of glutathione to mobilize secretions in the lung has been determined a safe and effective addition to treatment (Jones, 2011).

In a pilot study conducted by [name] at Lung Institute Nashville, after following approximately 100 treated patients, [name] discovered that within three months of treatment, 84 percent of patients reported improvement in their quality of life (Coleman, 2016). For millions of people suffering from COPD, a natural decline in pulmonary health is a harsh reality. Based on these results, stem cell therapy gives promise to improving their quality of life and slowing down the progression of disease.

At this time, autologous stem cell collection and administration is not commercially available and therefore is considered an investigational agent under the standards of the Texas Medical Board.

Lung Institute's collection and administration of stem cells as investigational agents in the state of Texas is part of a systematic program monitored under the strict oversight of Lung Institute's business associate and medical management services company, Regenerative Medical Solutions (RMS). Lung Institute and RMS are committed to the highest level of concern and caution for the welfare, safety and comfort of the patient to whom the cell therapy treatment is administered.

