## **4. RESEARCH QUESTIONS**

The research questions to be informed by this investigation are as follows:

1. Is the collection and administration of autologous stem cells for the treatment of chronic lung disease safe?
2. Does treatment with autologous stem cells for chronic lung disease improve measurements of pulmonary function (specifically FEV1)?
3. Does treatment with autologous stem cells for chronic lung disease improve the patient's perceived quality of life?

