10Mar2016 - version 2.0

LI-001

17.	
Clinic Staff takes blood supply to lab for processing and notifies Practitioner of Patient readiness.
 
 
• Has Clinic Staff completed the following? 
 
✓ Notified Practitioner of Patient readiness;
 
✓ Transfer blood drawn to the correctly labeled Harvest PRP cup for centrifuging; and
 
✓ Place PD Cup in centrifuge and press green start button or PRP start button.
 
 
 
 
➤ If NO > Step must be completed prior to proceeding.
 
➤ If YES > Proceed to Step 18 of this SOP

18.	
Practitioner reviews and conducts required pre-procedural protocols and renders physical exam.
 
 
• Has Practitioner reviewed the following prior to procedure and conducted the required? 
 
✓ Has Practitioner conducted and noted H&P or SOAP (Subjective; Objective; Assessment; Plan) on the Patient record; and
 
✓ Reviewed all required pre-procedural documentation?
 
 
 
 
➤ If NO > Step must be completed prior to moving forward with procedure.
 
➤ If YES > Proceed to Step 19 of this SOP

19.	
Clinic Staff will extract venous final product.
 
 
• Has Clinic Staff completed the following? 
 
✓ Draw PRP from the side compartment of PRP cup, identified by the white port.
 
✓ Use PRP to wash walls of PD Cup at least twice; and
 
✓ Extract into a 20ml syringe
 
 
 
 
➤ If NO > Step must be completed prior to proceeding.
 
➤ If YES > Proceed to Step 20 of this SOP

20.	
Clinic Staff administers final product.
 
 
• Has Clinic Staff completed the following? 
 
✓ Place venous final product (injected via the 20ml syringe referenced above) into the IV bag; and
 
✓ Open IV line (checking for sufficient flow and drip rate)
 
 
 
 
➤ If NO > Step must be completed prior to proceeding.
 
➤ If YES > Proceed to Step 21 of this SOP

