21.	
Clinic Staff conducts on-going oversight of Patient during administration.
 
 
• Has Clinic Staff confirmed the patency and flow are correct?
 
 
➤ If NO > Step must be completed prior to proceeding.
 
➤ If YES > Proceed to Step 22 of this SOP

22.	
Clinic Staff starts nebulizer treatment.
 
 
• Has Clinic Staff completed the following? 
 
✓ Place glutathione and saline into nebulizer medicine cup and provide Patient with instructions to begin nebulizing treatment; and
 
 
 
 
➤ If NO > Step must be completed prior to proceeding.
 
➤ If YES > Proceed to Step 23 of this SOP

10Mar2016 - version 2.0

LI-001

23.	
Clinic Staff discontinues IV line and nebulizer; and provide post care instructions.
 
 
• Has the Clinic Staff completed the following? 
 
✓ Turn off nebulizer when treatment completed;
 
✓ When final product has emptied IV bag, use normal saline flush to flush entire contents of IV line;
 
✓ Remove IV catheter;
 
✓ Place 2x2 gauze pad over site, affix coban bandage;
 
✓ Instruct Patient to remove gauze and coban after 20 to 30 minutes; and
 
✓ Dispose of supplies in designated biohazard containers.
 
 
 
 
➤ If NO > Step must be completed prior to proceeding.
 
➤ If YES > Proceed to Step 24 of this SOP

-----	---

24.	
Has Clinic Staff provides Patient with discharge folder and post-care instructions and answered any Patient questions or concerns?
 
 
• Has Clinic Staff advised the Patient of the below post-care instructions and ensured that they understand said instructions; answering any questions or concerns? 
 
✓ Briefly review and explain the discharge folder contents to Patient;
 
✓ Review LI follow-up procedures; and
 
✓ Review Patient Journals for quality of life outcome data.
 
 
 
 
➤ If NO > Step must be completed prior to proceeding.  ➤ If YES > Proceed to Step 25 of this SOP

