38.	
Clinic Staff prepares final product for administration via IV bag.
 
 
• Has Practitioner completed the following? 
 
✓ Remove 20ml syringe of bone marrow final product from Adi-Light;
 
✓ Inject bone marrow final product into 100ml normal saline IV bag; and
 
✓ Inject 20ml PRP syringe from top of clean box into same 100ml normal saline IV bag.
 
 
 
 
➤ If NO > Step must be completed prior to proceeding.
 
➤ If YES > Proceed to Step 39 of this SOP

39.	
Clinic Staff administers final product via IV.
 
 
• Has Clinic Staff completed the following? 
 
✓ Clean Hep-Lock site with alcohol prep pad;
 
✓ Affix IV tubing of final product contents to Hep-Lock catheter;
 
✓ Open IV line (checking for proper flow and drip rate).
 
 
 
 
➤ If NO > Step must be completed prior to proceeding.
 
➤ If YES > Proceed to Step 40 of this SOP

40.	
Clinic Staff conducts on-going oversight of Patient during administration.
 
 
• Has Clinic Staff confirmed the patency and flow are correct?
 
 
➤ If NO > Step must be completed prior to proceeding.
 
➤ If YES > Proceed to Step 41 of this SOP

41.	
Clinic Staff discontinues IV line.
 
 
• Has Clinic Staff completed the following? 
 
✓ When final product has emptied IV bag, use NS (normal saline) flush to flush entire contents of IV line;
 
✓ Remove IV catheter;
 
✓ Place 2x2 gauze pad over site, affix coban bandage
 
✓ Instruct Patient to remove gauze and coban after 20 to 30mins; and
 
✓ Dispose of supplies in designated biohazard containers.
 
 
 
 
➤ If NO > Step must be completed prior to proceeding.
 
➤ If YES > Proceed to Step 42 of this SOP

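### The venous SOPs prepare a product they name PRP, yet its results would be pooled and reported as the effect of autologous stem cells

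*Combined protocol and SAP*

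**What the plan says.** Section 4 poses all three research questions about autologous stem cells. The second reads: "Does treatment with autologous stem cells for chronic lung disease improve measurements of pulmonary function (specifically FEV1". Hypotheses 5a to 5c use the same name for the treatment. Section 1 treats stem cells and PRP as two things, both collected and both returned: "After the stem cells and platelet rich plasma have been isolated they are administered back to the patient". Policy CL-005 defines its procedures as autologous adult stem cell procedures and lists venous as one of them.

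The Venous Procedure SOP describes the preparation. Blood is drawn into a PRP kit, and Step 17 says "Place PD Cup in centrifuge and press green start button or PRP start button". Step 19 says "Draw PRP from the side compartment of PRP cup, identified by the white port", and Step 20 says "Place venous final product (injected via the 20ml syringe referenced above) into the IV bag". Step 22 adds an inhaled agent: "Place glutathione and saline into nebulizer medicine cup".

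For the analysis, section 12b names age, sex and diagnosis as sample characteristics and summarises FEV1 before and after treatment by mean, median and mode. It plans no breakdown by procedure. Section 2a states that every patient is treated under the same protocols.

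**The concern.** The treatment named in the questions and the product described in the venous SOP do not match, and nothing in the planned analysis would reveal it. A reader of the results would see one FEV1 summary and one adverse event summary under the heading of stem cell treatment. An unknown part of each would come from patients whose SOP yields something it calls PRP.

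Both efficacy and safety are affected. A pooled FEV1 change could be driven by either product. For question 1, a venous patient has a blood draw and an intravenous reinfusion, whereas a marrow patient also has an incision, trocar entry and two 30 ml aspirations (Bone Marrow SOP, Steps 26 to 29). If venous events are fewer, the pooled rate would understate the risk of marrow collection. Section 6 aims to generalise the FEV1 finding to all patients treated with autologous cell therapy, and section 12b says the study will inform the public and the medical community about stem cell treatment.

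**Working it through.** **Tracing the product**

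1. *Venous SOP.* Steps 4 and 7 open a PRP kit. Steps 15 and 16 draw about 55 ml of blood on the first day and about 30 ml on later days. Step 17 spins it with the green or PRP start button. Step 19 draws off PRP, and Step 20 infuses that syringe in the saline bag.
2. *Discharge SOP, venous branch (Steps 5 to 12).* The same sequence is followed: PRP kit, about 30 ml of blood, spin, draw off PRP, infuse, nebulised glutathione.
3. *Bone Marrow SOP.* Step 16 prepares a venous final product by the same kind of process and sets the syringe on the clean box. Step 38 first injects the bone marrow final product into the bag, then says "Inject 20ml PRP syringe from top of clean box into same 100ml normal saline IV bag". The sponsor's own text therefore identifies the venous final product as the PRP syringe and separates it from the marrow product.
4. *Stem cell steps.* No step in the venous or discharge SOP isolates, mobilises, counts or verifies stem cells. Section 13 mentions leukapheresis in a risk item, "this has been reported with leukapheresis (the process of separating stem cells from peripheral blood in the vein", but no supplied SOP contains that step.
5. *Glutathione.* Section 1 says it is given during treatment. The venous and venous discharge SOPs include it; the Bone Marrow SOP does not.

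So, by SOP, a venous patient receives a product named PRP plus nebulised glutathione, and a marrow patient receives marrow concentrate plus PRP.

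**What pooling does**

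The only design figure is the sample size of 200 in section 12a. It comes with no alpha, power, standard deviation, dropout rate or split by procedure, so it cannot be reproduced. The point does not depend on it.

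Let v be the venous share, which the documents do not give, and assume only the venous and marrow procedures are used.

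- Patients given a marrow product = 200(1−v)
- Pooled mean change = v × (venous change) + (1−v) × (marrow change)

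For illustration, take the 5% and 10% FEV1 increases in hypothesis 5a and let only one product have any effect:

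| v | Venous n | Marrow n | Pooled change, only marrow works (5% / 10%) | Pooled change, only venous works (5% / 10%) |
|---|---|---|---|---|
| 0% | 0 | 200 | 5 / 10 | 0 / 0 |
| 25% | 50 | 150 | 3.75 / 7.5 | 1.25 / 2.5 |
| 50% | 100 | 100 | 2.5 / 5 | 2.5 / 5 |
| 75% | 150 | 50 | 1.25 / 2.5 | 3.75 / 7.5 |
| 100% | 200 | 0 | 0 / 0 | 5 / 10 |

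At v = 50% the two opposite situations give the same pooled figure. The planned summary cannot tell them apart. These are weighted averages under assumed effects, not estimates of what the study will show.

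**The case against.** A reader might infer that venous patients receive no stem cells, that the study therefore tests the wrong intervention, and that questions 1 to 3 can be answered only from marrow patients. The documents do not support this, for three reasons.

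- **Absence is not shown.** No assay or cell count is reported for either product. The name PRP does not settle cell content, because Step 36 of the Bone Marrow SOP also uses it for part of the spun marrow.
- **The marrow product is not verified either.** Its SOP aspirates, filters, spins, exposes to light and infuses, with no step that identifies or counts stem cells. A test that disqualified venous patients would disqualify marrow patients too.
- **Venous is inside the sponsor's own definition.** Section 1 lists venous harvesting as a source of stem cells and PRP, and CL-005 lists venous as a stem cell treatment.

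Other points in the plan's favour are fair. Section 1 discloses PRP as part of the treatment. The section 12b list of characteristics is worded as open-ended, and both SOPs have the procedure captured in the electronic record. The leukapheresis text is a risk statement and is weak evidence about the study procedure. It would also be inaccurate to call PRP the only thing the two procedures share: CL-005 prescribes or recommends nebulisers or nebuliser solutions, supplements, rehabilitation and an incentive spirometer afterwards, and marrow Step 16 discards about 10 to 15 ml of plasma first, which venous Step 19 does not.

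What stands is the contradiction over what the venous product is, and an analysis that neither names procedure nor separates results by it.

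**Conclusion.** The point holds as a conflict between protocol and SOPs that carries through to the conclusions. As written, pooled efficacy and safety results would be attributed to autologous stem cells although they come in part from patients whose SOP yields a product named PRP, given with nebulised glutathione. The supportable statement is that these results cannot be attributed to stem cells on the evidence planned, not that stem cells are absent.

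The size is unknown because v is not stated. Across the full range of 0 to 100%, the number given a marrow product runs from 200 to 0. Step 2 of both SOPs directs patients on blood thinners or anti-arrhythmics to the venous procedure only, so some venous use is to be expected, but the documents do not support saying that it is the larger share. The two-part arithmetic assumes no adipose patients. If adipose is still offered, 200(1−v) counts all non-venous patients.

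**What to change.** 1. Reconcile section 1, section 13 and CL-005 with the SOPs on three matters: what the venous product is, whether glutathione belongs to both procedures, and whether adipose is still in the study. Sections 1, 9b and 11 still offer adipose, while the CL-005 revision history records its removal and the CL-005 attachment list has no adipose SOP.
2. Add procedure to the characteristics named in section 12b. Report FEV1, quality of life and adverse events separately by procedure. Present this as description: comorbidity and medication partly decide who has which procedure, so a difference between groups is not a treatment comparison.
3. In sections 4, 5, 6 and 12b and in all reports, name each result by what its SOP prepares: for venous, PRP with inhaled glutathione; for bone marrow, marrow concentrate plus PRP. Do not attribute venous or pooled results to stem cells unless the product is shown to contain them. A split table alone is not enough if the venous column is still headed stem cell treatment.

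No new patient data are needed, since procedure is already in the record. The cost is precision: with equal standard deviations, the standard error in a group of n is √(200/n) times that for all 200, which is 1.41 times for n = 100 and 2 times for n = 50. The change is also a protocol amendment, and the IRB notice requires approval before it is implemented.
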